Approximately, 30 subjects with angina, no obstructive CAD, and CMD invasively diagnosed by abnormal coronary flow reserve (CFR) and/or hyperemic microvascular resistance (HMR) will be enrolled in this single arm study. The primary objective is to evaluate the effect of CS narrowing using the Neovasc Reducer™ System on CFR and HMR at 4 months post Reducer implantation. Additional data will be collected on the adverse events and procedural success of the Reducer implantation procedure; as well as 4-months post-implant symptomatic and quality of life improvement as measured by the Canadian Cardiovascular Society (CCS) angina class, Seattle Angina Questionnaire short acting nitrates consumption frequency, functional capacity, intracardiac filling pressures, and ischemia as measured by exercise bicycle echocardiogram stress testing.

We hope that this study, the first of its kind in the USA using the CS Reducer as potential therapy for angina with no obstructive CAD (ANOCA) will address the therapeutic potential of CS narrowing for the treatment of CMD, an important unmet clinical need, and generate preliminary data for larger randomized phase 2 and 3 trials.

Study protocol

1- Introduction

This document is a human research study protocol. This study will be carried out in accordance with the applicable United States government regulations and Mayo Clinic research policies and procedures.

2- Background

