Figure 2: A) Improvement in Canadian Cardiovascular Society (CCS) class, Seattle Angina Questionnaire (SAQ) score, and 6 minute walk test (6MWT) at 4 months post CS Reducer implantation. B) Improved myocardial perfusion reserve index in a subgroup of patients. Adapted from Giannini F et al., JACC Cardiovascular Interventions ³².

More supportive data for the concept that increased CS pressure might improve microvascular function can be found in a very recent case presented by Tommaso Gori ³⁹ of a 61 year old man who presented with severe (CCS class 4) angina, non-obstructive CAD and elevated IMR. This patient was treated with Reducer implantation with consequent resolution of angina and dramatic reduction in IMR. Also, CS pressure elevation using pressure-controlled

intermittent CS occlusion (PISCO) in patients presenting with first anterior STEMI, resulted in improves microvascular function (reduction in IMR values) as well as reduction of infarct size (OxAMI-PISCO study)³³.

Safety and Procedural Success of CS Reducer System and Implantation Procedure

The safety and procedural success of CS Reducer implantation has been demonstrated in one randomized clinical trial and numerous observational studies done in Europe and Canada^{36, 37, 40, 41}. To date, no feasibility and efficacy studies have been done in the United States.

Potential complications of the procedure include dissection or perforation of the CS and device migration. However, as demonstrated in previous studies (COSIRA, n=52 and REDUCER-I, n=204) and non-published post-marketing commercial use in more than 1800 patients worldwide, no cases of mortality has been recorded and the rates of aforementioned complications, including myocardial infarction or permanent damage related to the device or procedure such as perforation, are very low (Table 1). Moreover, implantation procedure has very high success rates. The largest multicenter Italian registry reports 98.6% (n=139) procedural success with 2 patients (1.4%) failing due to unfavorable anatomy of the coronary sinus⁴¹. Summary of technical success data of CS Reducer implantation procedure from four previous studies is summarized in Table 2.

Table 1: Safety Data of CS Reducer System and Implantation Procedure³

Potential Complications (REDIFU-002 Reducer IFUCE Mark REV K)	Pre-Market Event Rate (COSIRA) N=52 n(%)	Post-Market Event Rate (REDUCER-I) N=204 n(%)	Post-Market Event Rate (Commercial Use) N=1840 n(%)

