Allergic reaction	0(0.00)	0(0.00)	0(0.00)

Arrhythmias (e.g. ventricular tachycardia (VT) or ventricular fibrillation (VF))	1(1.92)	4(1.96)	0(0.00)
Dissection (e.g. coronary sinus)	0(0.00)	4(1.96)	2(0.11)
Embolism (e.g. pulmonary or vessel)	0(0.00)	0(0.00)	0(0.00)
Conduction Disturbances	0(0.00)	0(0.00)	0(0.00)
Hypotension/hypertension	0(0.00)	0(0.00)	1(0.05)
Infection	0(0.00)	0(0.00)	0(0.00)
Access site complications	1(1.92)	1(0.49) ²	0(0.00)
Access site hematoma (not SAE)	Not reported	8(3.92)	Not reported
Access site minor bleed (not SAE)	Not reported	4(1.96)	Not reported
Ischemic events (e.g. myocardial infarction (MI) or unstable angina)	1(1.92)	0(0.00)	0(0.00)
Minor or major bleeding events (e.g. hemorrhage, cardiac tamponade, or pericardial effusion)	1(1.92)	1(0.49)	1(0.05)
Vascular event (e.g. pseudoaneurysm or thrombus)	0(0.00)	0(0.00)	0(0.00)
Perforation/rupture of coronary sinus, right atrium (RA), or internal jugular vein	0(0.00)	1(0.49)	3(0.16)
Pulmonary edema	0(0.00)	0(0.00)	0(0.00)
Reducer and/or coronary sinus occlusion (e.g. thrombus)	0(0.00)	0(0.00)	0(0.00)
Reducer fracture	0(0.00)	0(0.00)	0(0.00)
Reducer malposition, migration or embolization	2(3.85)	2(0.98)	10(0.54)
Respiratory failure	0(0.00)	0(0.00)	0(0.00)
Spasm of CS or jugular vein	0(0.00)	0(0.00)	0(0.00)
Cardiac valve injury (tricuspid)	0(0.00)	0(0.00)	0(0.00)
Myocardial damage	0(0.00)	0(0.00)	0(0.00)
Pyrogenic immunological or toxicological reaction	0(0.00)	0(0.00)	0(0.00)
Angina	0(0.00)	3(1.47)	0(0.00)
Chest pain ¹	1(1.92)	1(0.49)	0(0.00)

Minor neurologic event, including dysphagia, blurred vision, or TIA	0(0.00)	3(1.47)	0(0.00)
---	---------	---------	---------

¹*Chest pain has previously been categorized as angina and is therefore not currently included as an independent complication in the IFU*

²*Access Site Complications: one (1) access site complication due to device retrieval via the femoral vein*

³*Source: 022-CLN-012-2019 Rev A*

Table 2: Technical Success of CS Reducer Implantation Procedure

Study	N	Technical Success % (n)
COSIRA Treatment Arm	52	96.2 (50/52) ¹
FIM	15	93.3 (14/15) ²
REDUCER-I Overall	211	96.6 (204/211) ³
REDUCER-I Arm 1	161	95.6 (154/161) ³

¹ *Two subjects were not implanted – one due to inability to cannulate the CS and one due to inability to advance the guide catheter in the CS to the intended implant location*

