² *One subject experienced a migration post-implantation. The Reducer was noted to have moved during insertion but was inflated. As a result, the position of the deployed Reducer device was more proximal than desired. The dislodged Reducer then migrated and a 2nd Reducer was implanted without complications*

³ *Seven subjects were not implanted – 2 for CS dissection, 2 for tortuous anatomy, 1 for CS too small, 1 for inability to advance the guiding catheter, and 1 for movement of the Reducer while retracting the guidewire*

Accordingly, in this Phase-1 study we aim to evaluate the feasibility of CS Reducer implantation and its efficacy on invasively assessed microvascular function in ANOCA patients with CMD.

4- Study Hypothesis

In patients with ANOCA and invasive evidence of CMD, CS Reducer implantation is safe and will improve microvascular function as measured by CFR and HMR.

5- Aims

- 5.1 To evaluate the potential efficacy of CS Reducer implantation in ANOCA patients with CMD on microvascular function using invasive CFR and HMR assessments
- 5.2 To evaluate the potential efficacy of CS Reducer implantation in ANOCA patients with CMD on angina severity and frequency as assessed by CCS angina class and short-acting nitrates use, ischemia and exercise capacity as assessed by exercise bike echocardiographic stress test (EBEST), and quality of life as assessed by SAQ score.
- 5.3 To evaluate the potential efficacy of CS Reducer on left ventricular diastolic function and filling pressures as assessed by transthoracic echocardiographic parameters at peak exercise
- 5.4 To confirm the safety and feasibility of CS Reducer implantation patients with ANOCA and invasively documented CMD.
- 5.5 A successful demonstration in the proposed trial that CS Reducer implantation can be beneficial to patients with CMD will significantly advance the field of research aimed at FDA approval of the CS Reducer for treatment of ANOCA patients with CMD and opening the door to commercialization of CS Reducer for treatment of CMD, which is a critical unmet clinical need. If successful, the next stage of investigation will be the conduct of one or more pivotal registration studies to support FDA approval, and the proposed trial will provide information necessary to design these studies.

6- Study design

6.1 General Study Design:

- Prospective, single center, open label, single arm, clinical trial
- Number of participants: 30 subjects
- Duration of study: 4 months

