6.3 Secondary Endpoints

- Change in CCS angina class
- Change in the score of all 5 domains of the Seattle Angina Questionnaire for assessing quality of life
- Change in the consumption and frequency of short acting nitrates (spray or sublingual tablets)
- Change in EBEST parameters at 4 months compared with baseline (total exercise duration, time to 1 mm ST segment depression, evidence of ischemia, peak exercise stage, peak exercise diastolic function and filling pressures as measured by echocardiographic E/e', and exercise-induced symptoms)

- Procedural-related Major Adverse Cardiac Events (MACE) defined as: death, myocardial infarction, perforation of the CS, CS total occlusion, or need for urgent dilatation of the Reducer within 4 months of follow-up

7- Study Population:

Patients with chronic refractory angina (CCS class II-IV), no obstructive CAD (<50% stenosis in epicardial vessels and/or iFR>0.89 or FFR>0.8 in vessels with 50 to 70% stenosis), and documented CMD (CFR≤2.5 and/or HMR≥2.5) & or coronary blood flow (CBF) response to acetylcholine ≤ 50%. on clinically indicated coronary angiography and invasive coronary reactivity testing which uses Adenosine, Acetylcholine & Nitroglycerin as standard clinical practice

7.1 Inclusion Criteria:

- Age ≥ 18
- Able to provide written informed consent and willing to participate in all required study follow-up assessments
- Symptomatic CAD with refractory angina defined as CCS class II to IV, despite optimal tolerated medical therapy for more than 3 months.
- Abnormal coronary microvascular function indices: CFR≤2.5 and/or HMR≥2.5 & or coronary blood flow (CBF) response to acetylcholine ≤ 50%.

7.2 Exclusion Criteria:

- Recent (within 3 months) acute coronary syndrome
- Recent (within 6 months) percutaneous coronary intervention revascularization by stent
- Patients with prior coronary artery bypass surgery

- Unstable angina (recent onset angina, crescendo angina, or rest angina with ECG changes) during the last 30 days
- Subjects in cardiogenic shock (systolic pressure < 80mm/Hg, on vasopressors or intraaortic counter pulsation) at the time of consenting. Subjects who recover from cardiogenic shock by the time of consenting are eligible.
- Obstructive CAD on coronary angiography (>70% stenosis or 50-70% stenosis with $iFR \leq 0.89$ or $FFR \leq 0.8$ in epicardial artery)
- Inability to perform invasive coronary flow evaluation and/or measure CFR and HMR in the LAD
- Severe valvular heart disease

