11.8 Schedule of Study Procedures and Assessments

Study Procedure/ Assessment	Screening	Enrolment/ Pre-Implant	Implant Day	Post-Implant			
Days	-30	-5 to -1	0	30	60	90	120

Windows				± 4	±7	±7	±14
Eligibility criteria	X						
Informed consent	X						
Medical history	X						
Vital signs	X	X	X				X
12-lead ECG	X	X	X				X
Standard laboratory tests including hematology, blood chemistry, liver function tests, CRP and creatinine, urinalysis.		X*					X
EBEST		X					X
CS Reducer Implant			X				
CCS Angina Class		X		X	X	X	X
SAQ		X		X	X	X	X
Coronary angiography to measure CFR and HMR							X
Physical exam	X						
Limited physical exam			X				
Adverse events	X	X	X	X	X	X	X

Concomitant medications	X						
-------------------------	----------	----------	----------	----------	----------	----------	----------

- a. CS Reducer will be implanted in the coronary sinus through right (preferably, or left internal jugular venous access)
- b. The patient will receive a phone call from the study coordinator to collect information on adverse events, angina class, SAQ, and concomitant medications.
- c. Vital signs will be measured prior to implant and every 8 hours until discharge
 - * Standard pre-procedural laboratory tests including hematology and blood chemistry including creatinine. Liver function tests, CRP, and urinalysis only at Day 120.

12- Statistical Plan

The effect of the CS Reducer implantation on microvascular function will be evaluated by the change in measured CFR and HMR at 4 months follow-up compared to baseline pre-CS Reducer implantation. Statistical analysis of the absolute and percent change in CFR and HMR measurements at follow-up will be done. Analysis of the delta change in CFR and HMR will also be performed. Change in angina intensity and frequency, and quality of life, will be evaluated by analyzing the change in CCS angina class, SAQ score in all five domains, and antianginals need and frequency from baseline to follow-up. Change in functional capacity will be evaluated as the change in baseline to follow-up EBEST total exercise duration, peak exercise stage, exercise-induced symptoms, and ischemic ECG and echocardiographic findings. Change in diastolic function and filling pressures will be evaluated as baseline to follow-up change in resting and peak exercise echocardiographic E/e' ratio.

All-completed population: Only subjects who completed ALL study related procedures and follow-up will be included in analysis.

13- Safety and Adverse Events

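### The listed safety endpoint omits device migration and CS dissection, technical success is not an endpoint, and the completers-only rule would drop failed implants

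*Combined protocol and SAP*

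**What the plan says.** - **Safety endpoint.** Section 6.3 (and the synopsis) gives one, procedure-related MACE, with these components: "death, myocardial infarction, perforation of the CS, CS total occlusion, or need for urgent dilatation of the Reducer within 4 months of follow-up". Section 11.1 mentions primary safety endpoints in passing, but none is defined anywhere.
- **Known complications.** Section 3, under the heading on safety and procedural success, states: "Potential complications of the procedure include dissection or perforation of the CS and device migration". Table 1 has a row for "Reducer malposition, migration or embolization", one for dissection, one for perforation or rupture, and one for occlusion.
- **Feasibility.** It is in the study title and in Aim 5.4: "To confirm the safety and feasibility of CS Reducer implantation patients with ANOCA and invasively documented CMD". The Project Summary says that data will be collected on adverse events and on "procedural success of the Reducer implantation procedure", but neither section 6.2 nor section 6.3 lists technical or procedural success.
- **Analysis.** Section 12 covers flow measures, symptoms and exercise testing, for example: "Statistical analysis of the absolute and percent change in CFR and HMR measurements at follow-up will be done". It has no analysis of MACE, adverse events or technical success. Its one analysis population is restricted to patients who finished every study procedure and the whole of follow-up.
- **Size.** Section 6.1: "Number of participants: 30 subjects", in a single arm. No performance goal, margin or precision target is given.

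**The concern.** Of the three procedure complications that the protocol itself names, the safety endpoint counts one. A migrated device or a dissected CS enters MACE only if it goes on to cause death, myocardial infarction, perforation, total occlusion or urgent dilatation. The trial could therefore report no MACE although a device migrated or a CS was dissected.

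Feasibility has an aim but no measure. Read literally, section 12 makes this worse: a patient in whom the device could not be implanted has not completed all procedures and leaves the analysis, so the analysed patients would show apparently full technical success whatever happened in the catheterization laboratory. The same rule would remove a patient who dies before day 120, although death is a MACE component.

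Aim 5.5 says that the trial is to inform the design of pivotal studies. Device-event and implant-failure rates are among the figures that those studies would need.

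**Working it through.** **1. Table 1 counts** (section 3). The printed percentages for these rows reproduce as n/N, for example 2/52 = 3.85%, 4/204 = 1.96% and 10/1840 = 0.54%.

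| Row | COSIRA (52) | REDUCER-I (204) | Commercial (1,840) | Pooled (2,096) |
|---|---|---|---|---|
| Malposition, migration, embolization (not in MACE) | 2 | 2 | 10 | 14 (0.67%) |
| Dissection (not in MACE) | 0 | 4 | 2 | 6 (0.29%) |
| Perforation or rupture (in MACE) | 0 | 1 | 3 | 4 (0.19%) |
| Occlusion (in MACE) | 0 | 0 | 0 | 0 |

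The ischemic-events row adds 1 (COSIRA). It mixes infarction with unstable angina, so the MACE components that have a Table 1 row total 4 to 5. Urgent dilatation has no row. By column the order varies: COSIRA has no dissections, and in commercial use perforation (3) exceeds dissection (2).

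**2. Chance that at least one omitted event occurs in 30 patients**, 1 − (1 − p)^30, taking p as migration row plus dissection row and assuming that no patient had both:

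- COSIRA, 2/52 = 3.85%: 69%.
- REDUCER-I, 6/204 = 2.94%: 59%. The 204 equals the number successfully implanted in Table 2; with all 211 as denominator, 6/211 = 2.84% and the chance is 58%.
- Commercial use, 12/1840 = 0.65%: 18%.

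For comparison, the MACE components with a row in REDUCER-I total 1/204 = 0.49%, a 14% chance of at least one.

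**3. Technical failure.** Table 2 gives 204/211 for REDUCER-I, so 7/211 = 3.3% failed. Expected in 30: 30 × 7/211 = 1.0. Chance of at least one: 1 − (204/211)^30 = 64%. The Table 2 footnotes link this to the omitted events: two of the seven REDUCER-I failures were for CS dissection and one for movement of the device. The first-in-man failure was a migration that led to a second device.

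**4. What 30 patients can show, whatever the endpoint contains.**

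- 0/30 events, one-sided 95% upper bound: 1 − 0.05^(1/30) = 9.5%.
- 0/30 events, two-sided 95% upper bound: 1 − 0.025^(1/30) = 11.6%.
- 1/30 events, exact two-sided upper bound: 17.2%.
- 30/30 successes, two-sided lower bound: 0.025^(1/30) = 88.4%.
- 29/30 successes, exact two-sided interval: 82.8% to 99.9%.

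The 9.5% bound is above the highest migration-row rate in any column, 3.85%. The plan states no rate to exclude. If one assumed 5% or 2%, zero events would be needed in 59 or 149 patients: ln(0.05)/ln(1 − rate), rounded up.

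**The case against.** The strongest reply is that these events are not lost. All adverse events are collected for 4 months (sections 6.1 and 13.10), serious ones include life-threatening procedural complications and any hospitalization after implant (13.3), an independent DSMB reviews them (13.14), and enrollment pauses after six patients for a one-month safety check (7.3). Procedural success data are to be collected. This stands: a reader might infer that a migration or dissection would go unseen, and the documents do not support that.

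It can also be said that a composite of major events is chosen by severity, not by past frequency. Omitting dissection or malposition without consequence is then defensible, and including occlusion despite zero past cases is no fault. This stands too, and is why MACE itself should not be changed.

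The pooled Table 1 counts need care. Commercial use supplies 1,840 of the 2,096 patients; the migration row includes malposition; the dissection row gives the CS only as an example; and the order is not the same in each column. So the pooled counts of 20 omitted against 4 or 5 included events should not be read as a firm ratio.

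Finally, the Project Summary describes the study's output as preliminary data, which makes *confirm* look like loose wording rather than a formal claim. That is fair, but section 4 also hypothesizes that implantation is safe, and no criterion is given by which either statement could be judged.

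What the reply does not meet: recording an event is not the same as prespecifying how it is reported and over which patients, and nothing elsewhere overrides the completers-only sentence in section 12.

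**Conclusion.** The point holds as a gap in prespecified endpoints and in the analysis set. The one listed safety endpoint omits two of the three complications that the protocol names; feasibility has no endpoint; and section 12 as written would remove failed implants from analysis. The gap is likely to matter: the chance of at least one omitted event in 30 patients is 18% at commercial rates and 59% to 69% at the rates of the two studies, and about one failed implant is expected at the REDUCER-I rate. These figures assume that past rates carry over to patients without obstructive disease and that the Table 1 rows do not overlap.

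The wording of Aim 5.4 is a separate matter. A reader might infer that 30 patients cannot confirm safety because the composite is too narrow. That does not follow: widening it leaves the bound for 0/30 at 9.5% (one-sided) or 11.6% (two-sided). The limit comes from the sample size and the absence of any performance criterion.

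**What to change.** 1. Keep MACE in section 6.3 as defined.
2. Add to section 6.3 and the synopsis a separate descriptive device and procedure safety endpoint, reported by component: malposition, migration or embolization; CS dissection; perforation.
3. Add technical success, with a definition. The definition should say whether a migration followed by a second device counts as failure, as it did in the first-in-man row of Table 2.
4. Add one sentence to section 12: MACE, the device and procedure endpoint, and technical success are analysed in all patients with an attempted implant. Say when an attempt begins: three of the seven REDUCER-I failures (two tortuous anatomy, one CS too small) were on anatomical grounds of the kind that section 7.2 lists as exclusions, and section 11 lists no CS angiogram before implant day.
5. Report each with an exact two-sided 95% confidence interval.
6. In Aim 5.4 replace *confirm* with *estimate*, or state and justify a performance criterion. In section 11.1 define or delete the reference to primary safety endpoints.

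The cost is wording, two descriptive tables and one analysis-set sentence. The protocol already commits to collecting the data, and the sample size does not change unless a performance criterion is chosen.

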IMR, but also reduces infarct size (OxAMI-PISCO study) ³³. It has been suggested that CS narrowing leads to increased backwards pressure that causes slight dilatation and a consequent reduction in the resistance to flow in the arterioles of the ischemic sub-endocardial myocardium. This subsequently causes a redistribution of blood from the less ischemic subepicardium to the more ischemic subendocardium ³⁴. The enhancement of blood flow within the ischemic subendocardial layers of the myocardium reduces ischemia and leads to symptoms relief and improved quality of life.

3- The Coronary Sinus Reducer

The Neovasc Reducer™ System (Neovasc Inc., Richmond, B.C., Canada), hereby referred to as the CS Reducer in this protocol, is a CE marked, balloon-mounted, hourglass-shaped stainless steel mesh for percutaneous transvenous implantation into the coronary sinus. The CE Mark indication for use is in patients with refractory angina pectoris and objective evidence of reversible myocardial ischemia, who have limited treatment options and are thus referred to as ‘no-option’ patients. These patients are either not amenable to, or are high risk for, revascularization by coronary artery bypass grafting (CABG) or by percutaneous coronary intervention (PCI). The Reducer System is intended to create a permanent and controlled narrowing of the coronary sinus (CS), to improve perfusion to ischemic myocardium. As discussed above, CS Reducer is emerging as a potentially effective therapy for disabling angina in patients (n=104) with obstructive CAD and no revascularization options ³¹ with objective evidence to support reduction in myocardial ischemia on MRI, SPECT and dobutamine stress echocardiography ³⁵⁻³⁷ and improvement in diastolic left ventricular function ³⁸. However, the role of the CS Reducer in patients with microvascular angina and no obstructive CAD remains unclear. Observational data from a first-in-human

(n=8) preliminary study of compassionate CS Reducer implantation for presumed refractory microvascular angina post at least one PCI procedure and no residual epicardial obstructive disease demonstrated improvement in CCS class, SAQ score, and 6MWT at 4 months post implant ³², with improved myocardial perfusion reserve index in a subgroup of patients (n=3) suggestive of improved microvascular function (Figure 2). Yet, CS Reducer has not yet been specifically tested in ANOCA patients with invasively documented microvascular dysfunction.

[figure not shown]

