The first six patients will be sequentially enrolled, and subsequent enrollment will be held until one-month follow-up. Provided there are no safety concerns at this time, enrollment will continue. Staggered enrollment will help ensure that subsequent patients are not enrolled until there is adequate follow-up and safety of initial patients. The patients for this study will be recruited through the outpatient clinics in the Department of cardiology, including the Chest Pain and Coronary Physiology Clinic and the Coronary Artery Disease Clinic at Mayo Clinic. There have been over 35,000 patients seen in the Cardiovascular Division at Mayo Clinic yearly. There are over 6,000 cardiac catheterizations performed yearly in the cardiac catheterization lab. As a part of our clinical practice, patients with angina referred to the catheterization laboratory for a clinically indicated coronary angiography and found to have non-obstructive CAD are undergoing a comprehensive coronary reactivity testing including assessment of microvascular function with CFR and HMR. Typically, 8-10 patients per month undergo this comprehensive coronary physiology study. This will be mediated through referring physicians. Patients that meet inclusion and exclusion criteria will be considered for recruitment in the study.

7.4 When and How to Withdraw Subjects:

Subjects will be withdrawn from the study prior to completion of all study related procedures if 1 of 5 consecutive patients have serious adverse safety events.

7.5 Data Collection and Follow-up for Withdrawn Subjects:

Even though a subject has withdrawn from the study, it may be important to collect some follow-up or survival data on such subjects throughout the protocol defined follow-up period. Such data is important to the integrity of the final study analysis since early withdrawal could be related to the safety profile of the study device and/or implantation procedure. If a subject withdraws consent to participate in the study, for subject safety reasons, we will make attempts to obtain permission to collect follow up information whenever possible.

[figure not shown]

Figure 3: Flow chart of the study design. CAD: coronary artery disease; CMD: coronary microvascular dysfunction; CRT: coronary reactivity testing; CFR: coronary flow reserve; HMR: Hyperemic microvascular resistance; CCS: Canadian cardiovascular society; SAQ: Seattle angina questionnaire; EBEST: Exercise bike echocardiographic stress test.

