13.3 Serious Adverse Event

Adverse events are classified as serious or non-serious. Serious problems/events can be well defined and include;

- Death
- Myocardial infarction
- Stroke
- Life threatening adverse procedural or periprocedural complications
- Any hospitalizations post CS Reducer implantation
- Inpatient, new, or prolonged; disability/incapacity

and/or per protocol may be problems/events that in the opinion of the sponsor-investigator may have adversely affected the rights, safety, or welfare of the subjects or others, or substantially compromised the research data. Serious adverse events are ones that may result in death or can be life-threatening, requires extended hospitalization, significant disability, meaning a substantial disruption to the person's ability to conduct normal life functions. This excludes experiences of minor medical significance such as headache, nausea, vomiting, influenza, diarrhea, accidental trauma, which may disrupt daily functions but is not substantial. Medical or scientific judgment should be exercised when deciding whether reporting is appropriate in situations.

All adverse events that do not meet any of the criteria for serious, should be regarded as non-serious adverse events.

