13.14 Stopping Rules

The principal investigator will review all serious adverse events and be involved in the decision to stop the study. The study will be stopped if 3/5 patients experience serious adverse events deemed secondary to the study device, including death, cardiovascular mortality, bleeding, stroke or sepsis thought to be secondary to CS Reducer implantation. Given that the CS Reducer has no FDA approved indication yet, and to ensure independent review and reporting of adverse events and determine if study stopping criteria have been met, a DSMB committee will be formed. The committee will be formed of 3 independent members: [name], an independent interventional and structural heart disease expert will be a member and chair the committee, and the remaining 2 members will be an independent cardiologist who evaluates and manages patients with coronary microvascular dysfunction at Mayo Chest Pain Clinic, and an independent Mayo Clinic statistician. These members will be named prior to initiation of the study.

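### Section 7.4 withdraws subjects after a serious adverse event without saying which ones, and the completers-only rule in Section 12 then removes them from the efficacy analysis

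*Combined protocol and SAP*

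**What the plan says.** Section 7.4 is a single sentence, which has subjects "withdrawn from the study prior to completion of all study related procedures if 1 of 5 consecutive patients have serious adverse safety events". It sets no device-relatedness condition and does not identify the subjects who leave.

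Section 12 defines one analysis population: "Only subjects who completed ALL study related procedures and follow-up will be included in analysis". The analyses listed there are CFR and HMR, CCS class, SAQ, antianginal use, the EBEST measures and E/e'. MACE and adverse events are not listed, and no safety population is named.

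Section 7.5 deals with withdrawn subjects. It begins cautiously ("it may be important to collect some follow-up or survival data on such subjects"), then says that these data matter to the integrity of the final analysis because early withdrawal may be linked to the safety of the device or procedure.

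Four other places bear on the point:
- Section 13.3 lists "Any hospitalizations post CS Reducer implantation" among serious events. Section 13.9 exempts planned and elective admissions and some admissions for the target disease.
- Section 6.3 has procedure-related MACE as a secondary endpoint: "death, myocardial infarction, perforation of the CS, CS total occlusion, or need for urgent dilatation of the Reducer within 4 months of follow-up".
- Section 3 describes the device as intended to create a "permanent and controlled narrowing of the coronary sinus", and aim 5.4 is "To confirm the safety and feasibility of CS Reducer implantation".
- Section 13.14 is a separate rule for the whole study: "The study will be stopped if 3/5 patients experience serious adverse events deemed secondary to the study device". It also sets up a DSMB.

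**The concern.** Sections 7.4 and 12 together make inclusion in the analysis depend on a safety outcome that arises after implantation. A patient who has a serious event but could still attend the 4-month visit is taken out before completing, and is then excluded for not having completed. If the group of five or all ongoing subjects are meant, patients who had no event are removed as well.

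This is a single-arm study of 30, so there is no control group in which the same selection would show. If patients with serious events tend to respond less well, the observed change in CFR and HMR will look better than it was among the patients implanted. Withdrawal does not end exposure to a permanent implant, so stopping follow-up early also loses information on an aim that the protocol states. Section 7.5 recognises the value of these data, but Section 12 has no population that would use them.

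**Working it through.** The plan attaches no operating characteristic to the 1-of-5 rule, so there is no figure to reproduce. The finding rests on the text; the arithmetic only shows its size.

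**Step 1. The chain of rules.** A single qualifying event is already 1 in a run of five, so one event meets the trigger (7.4). The subject or subjects are withdrawn before finishing all procedures (7.4). Only subjects who finished all procedures and follow-up are analysed (12). Exclusion follows from the wording, with no assumed rate.

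**Step 2. Number left after one event, N = 30 (Section 6.1).**
- Only the affected patient leaves: 30 − 1 = 29.
- The five leave, none having completed: 30 − 5 = 25.
- All ongoing subjects leave: depends on accrual, so no figure can be given.

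**Step 3. How often the trigger could be met.** The documents give no all-cause serious-event rate for these patients, so the per-patient 4-month rate p is assumed, with patients independent. The chance of at least one event in 30 is 1 − (1 − p)^30. Expected withdrawals are 30p if only affected patients leave, and 30[1 − (1 − p)^5] if whole blocks of five leave (six separate blocks).

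| Assumed p | Trigger met at least once | Affected only, 30p | Blocks of five |
|---|---|---|---|
| 1% | 26.0% | 0.3 | 1.5 |
| 5% | 78.5% | 1.5 | 6.8 |
| 10% | 95.8% | 3.0 | 12.3 |

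The last two columns are upper bounds for their readings. A patient who dies is lost whatever 7.4 says, and an event at or after the day-120 procedures comes too late for withdrawal before completion.

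**Step 4. MACE, conditional on the completers-only sentence applying to it.** Take one non-fatal procedure-related infarction among 30, with only that patient withdrawn. Intervals are Clopper-Pearson 95%.
- All 30: 1/30 = 3.3%. The lower limit is 1 − 0.975^(1/30) = 0.08%, shown as 0.1%. The upper limit u solves (1 − u)^30 + 30u(1 − u)^29 = 0.025, giving 17.2%.
- Completers: 0/29 = 0%. The upper limit is 1 − 0.025^(1/29) = 11.9%.

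Infarction is the useful example because it is on both the serious list (13.3) and the MACE list (6.3), and a patient who survives one might otherwise complete.

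**The case against.** The strongest reply is that the safety data are not lost. Section 13 requires every adverse event to be recorded and followed, serious events to be reported within 24 hours, and adverse effects to be summarised yearly for the FDA; a DSMB reviews events. Section 12 never mentions MACE, so its completers-only sentence may have been meant for efficacy alone. This stands. A reader might infer that the plan will report MACE as zero after an infarction; the documents do not establish that, and the 0/29 figure is conditional. What remains is that no denominator for MACE is stated anywhere.

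Second, Section 7.5 expects safety-related withdrawal and says the data matter to the final analysis. That is so, and it would be unfair to say the protocol is indifferent to them. But Section 12 provides no analysis that uses them.

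Third, the term for the triggering event in 7.4 is not defined in Section 13. Equating it with every non-exempt hospitalisation in 13.3 is plausible but is an inference. Likewise, the loss of five patients per event is only one reading of the plural.

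Fourth, much of the harm comes from Section 12 itself: deaths would be excluded even without 7.4. This also stands, and is why the fix has to change both sections.

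A reader might also think that 7.4 and 13.14 contradict each other. They do not: one withdraws subjects, while the other stops the study at a higher threshold for device-related events.

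**Conclusion.** The point holds for the efficacy analyses on the text alone. As written, 7.4 and Section 12 remove implanted patients from the CFR/HMR and clinical analyses because of a safety event, and 7.4 does not say which patients those are. At the least this costs one patient in 30 per event. The direction of any bias in CFR or HMR cannot be determined from the documents.

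For MACE the point is conditional: if the completers-only sentence applies, 1/30 (3.3%, 0.1% to 17.2%) becomes 0/29 (0% to 11.9%) in the analysis, while the event itself stays on record under Section 13.

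Confidence is high for the gap in the text and lower for its size, because the trigger frequencies rest on assumed rates and independence. This should be fixed before the analysis.

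**What to change.** 1. **Section 7.4:** delete the withdrawal trigger. Refer such events to the DSMB already planned in 13.14.
2. **Follow-up:** follow every implanted subject to 4 months unless the subject withdraws consent or a specific study procedure is unsafe for that subject. In the latter case omit only that procedure and keep the rest of the follow-up.
3. **Section 12:** state that MACE and adverse events are reported for all subjects in whom an implant was attempted. Analyse CFR/HMR and the clinical endpoints in all implanted subjects who have the relevant 4-month measurement, in place of the requirement to have completed everything.

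The enrolment hold after the first six patients (7.3) and the 3/5 stopping rule (13.14) can stay as they are; this point needs no new enrolment pause.

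The cost is amendment wording, DSMB review of each referred event, and some patients with events remaining due for the 4-month visit, including repeat angiography unless it is unsafe for them. No extra patients are needed. The change does not recover 4-month CFR/HMR for patients who die or cannot safely be retested, but they would still count in the safety results, and patients not retested would still contribute the clinical measures they have.
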